##### **8.4.2 Electrocardiograms (ECGs)**

Subject must be in supine position in a rested and calm state for at least 5 minutes before ECG assessment is conducted. If the subject is unable to be in the supine position, the subject should be in most recumbent position as possible. The ECG must include the following measurements: Heart Rate, QRS, QT, QTc, and PR intervals. The PI or (eg, designated site physician, central reader) will review all ECGs. Once signed, the original ECG tracing will be retained with the subject's source documents. At the request of the sponsor, a copy of the original ECG will be made available to Amgen.

##### **8.4.3 Clinical Laboratory Assessments**

Refer to Section 11.2 for the list of clinical laboratory tests to be performed and to the Schedule of Activities (Section 1.3) for the timing and frequency.

The investigator is responsible for reviewing laboratory test results and recording any clinically relevant changes occurring during the study in the Events CRF. The investigator must determine whether an abnormal value in an individual study subject represents a clinically significant change from the subject's baseline values. In general, abnormal laboratory findings without clinical significance (based on the investigator's judgment) are not to be recorded as adverse events. However, laboratory value changes that require treatment or adjustment in current therapy are considered adverse

events. Where applicable, clinical sequelae (not the laboratory abnormality) are to be recorded as the adverse event.

All protocol-required laboratory assessments, as defined in Section [11.2](#), must be conducted in accordance with the laboratory manual and the Schedule of Activities ([Table 1-1](#)).

#### **8.4.4 Survival Status**

Survival status must be obtained for all subjects within the limits of local law. This includes subjects who may have discontinued study visits with or without withdrawing consent and should include interrogation of public databases, if necessary. If deceased, the date and reported cause of death should be obtained.

#### **8.4.5 Other Safety**

Left ventricular ejection fraction will be assessed by echocardiography at screening. **For subjects developing COVID-19 during screening period and following screening ECHO assessments, consider repeating ECHO following resolution. For subjects developing COVID-19 during treatment period, consider whether ECHO should be performed before resuming investigational product treatment to rule out COVID-19 myocarditis especially in subjects with cardiac comorbidities.**

#### **8.4.6 Adverse Events and Serious Adverse Events**

The method of recording, evaluating, and assessing causality of adverse events and serious adverse events and the procedures for completing and transmitting serious adverse event reports are provided in Section [11.4](#).

##### **8.4.6.1 Time Period and Frequency for Collecting and Reporting Safety Event Information**

###### **8.4.6.1.1 Adverse Events**

The adverse event grading scale to be used for this study will be the CTCAE and is described in Section [11.4](#). CRS, which will be graded using the criteria referenced in the publication by Lee et al (2019) (see Section [11.10](#)) and TLS, which will be graded according to the Cairo Bishop criteria referenced in the publication by Coiffier et al (2008) (see Section [11.11](#)), and ICANS will be using the criteria referenced in the publication by Lee et al (2019) (see Section [6.2.1.6.1.1](#)).

The investigator is responsible for ensuring that all adverse events observed by the investigator or reported by the subject that occur from the time of consent through the safety follow-up visit 90 (+ 7) days after the last dose of study drug, are reported using

the Events CRF. For subjects that start a new line of therapy before the 90 (+ 7) day follow-up visit, all adverse events should be collected and reported through 30 days post last dose of investigational product/protocol-required therapies or until the subject begins a new line of therapy, whichever occurs later.

#### **8.4.6.1.2      Serious Adverse Events**

The investigator is responsible for ensuring that all serious adverse events observed by the investigator or reported by the subject that occur **from the time of** consent through the safety follow-up visit **90 (+ 7) days after the last dose of study drug**, are reported using the Events CRF. **For subjects that start a new line of therapy before the 90 (+ 7) day follow-up visit, all serious adverse events should be collected and reported through 30 days post last dose of investigational product/protocol-required therapies or until the subject begins a new line of therapy, whichever occurs later.**

All serious adverse events will be collected, recorded and reported to the sponsor or designee immediately and no later than 24 hours of the investigator's awareness of the event, as indicated in Section 11.4. The investigator will submit any updated serious adverse event data to the sponsor immediately and no later than 24 hours of it being available.

Since the criteria the CTCAE grading scale differs from the regulatory criteria for serious adverse events, if adverse events correspond to grade 4 CTCAE toxicity grading scale criteria (eg, laboratory abnormality reported as grade 4 without manifestation of life-threatening status), it will be left to the investigator's judgment to also report these abnormalities as serious adverse events. For any adverse event that applies to this situation, comprehensive documentation of the event's severity must be recorded in the subject medical records.

#### **8.4.6.1.3      Serious Adverse Events After the Protocol-Required Reporting Period**

During the long-term follow-up period if the investigator becomes aware of serious adverse events (regardless of causality) after the protocol-required reporting period (as defined in Section 8.4.6.1.2) is complete, then these serious adverse events will be reported to Amgen. The investigator will report serious adverse events to Amgen immediately and no later than 24 hours following the investigator's awareness of the event on the Events CRF.

There is no requirement to actively monitor study subjects after the study has ended with regards to study subjects treated by the investigator. However, if the investigator becomes aware of serious adverse events suspected to be related to investigational product, then these serious adverse events will be reported to Amgen immediately and no later than 24 hours following the investigator's awareness of the event.

Serious adverse events reported **after the end of the study** will be captured within the safety database as clinical trial cases and handled accordingly based on relationship to investigational product.

If further safety related data is needed to fulfill any regulatory reporting requirements for a reportable event, then additional information may need to be collected from the subject's records after the subject ends the study.

#### **8.4.6.2        Method of Detecting Adverse Events and Serious Adverse Events**

Care will be taken not to inquire introduce bias when detecting adverse events and/or serious adverse events. Open-ended and non-leading verbal questioning of the subject is the preferred method to about adverse event occurrence.

#### **8.4.6.3        Follow-up of Adverse Events and Serious Adverse Events**

After the initial adverse event/serious adverse event report, the investigator is required to proactively follow each subject at subsequent visits/contacts. All adverse events and serious adverse events will be followed until resolution, stabilization, until the event is otherwise explained, or the subject is lost to follow-up (as defined in Section 7.3).

Further information on follow-up procedures is given in Section 11.4.

All new information for previously reported serious adverse events must be sent to Amgen immediately and no later than 24 hours following awareness of the new information. If specifically requested, the investigator may need to provide additional follow-up information, such as discharge summaries, medical records, or extracts from the medical records. Information provided about the serious adverse event must be consistent with that recorded on the Events CRF.

#### **8.4.6.4        Regulatory Reporting Requirements for Serious Adverse Events**

If subject is permanently withdrawn from protocol-required therapies because of a serious adverse event, this information must be submitted to Amgen.

Prompt notification by the investigator to the sponsor of serious adverse events is essential so that legal obligations and ethical responsibilities towards the safety of subjects and the safety of a study treatment under clinical investigation are met.

The sponsor has a legal responsibility to notify both the local regulatory authority and other regulatory agencies about the safety of a study treatment under clinical investigation. The sponsor will comply with country-specific regulatory requirements relating to safety reporting to the regulatory authority, IRBs/IECs, and investigators. The sponsor holding the relevant Investigational New Drug/Clinical Trial Application for either AMG 340 or [REDACTED] or F-FDG has a legal responsibility to notify both the local regulatory authority and other regulatory agencies about the safety of AMG 340 or [REDACTED] or F-FDG, respectively, under clinical investigation. The sponsor will comply with country-specific regulatory requirements relating to safety reporting to the regulatory authority, IRBs/IECs, and investigators.

Individual safety reports must be prepared for suspected unexpected serious adverse reactions according to local regulatory requirements and sponsor policy and forwarded to investigators as necessary.

An investigator who receives an individual safety report describing a serious adverse event or other specific safety information (eg, summary or listing of serious adverse events) from the sponsor will file it along with the IB and will notify the IRB/IEC, if appropriate according to local requirements.

Amgen will prepare a single Development Safety Update Report (DSUR) (also referred to as Annual Safety Report [ASR] in the European Union) for the Amgen Investigational Product. In order to ensure that consolidated safety information for the trial is provided, this single DSUR will also include appropriate information on any other investigational products used in the clinical trial, if applicable.

#### **8.4.6.5 Safety Monitoring Plan**

Subject safety will be routinely monitored as defined in Amgen's safety surveillance and signal management processes.

#### **8.4.6.6 Pregnancy and Lactation**

Details of all pregnancies in female partners of male subjects will be collected after the start of study treatment and until 6 months after last dose of investigational product/protocol-required therapies.

If a pregnancy is reported, the investigator is to inform Amgen immediately and no later than 24 hours of learning of the pregnancy and is to follow the procedures outlined in Section 11.5. Amgen Global Patient Safety will follow-up with the investigator regarding additional information that may be requested.

Abnormal pregnancy outcomes (eg, spontaneous abortion, fetal death, stillbirth, congenital anomalies, and ectopic pregnancy) are considered serious adverse events.

Further details regarding pregnancy are provided in Section 11.5.

Additional on-treatment pregnancy testing may be performed at the investigator's discretion or as required per local laws and regulations.

### **8.5 Pharmacokinetic Assessments**

Blood samples will be collected for measurement of serum concentrations of AMG 340 as specified in the Schedule of Activities (Section 1.3). Instructions for the collection and handling of biological samples will be provided by the sponsor. The actual date and time (24-hour clock time) of each sample will be recorded.

[figure not shown]
### **8.7 Antibody Testing Procedures**

[figure not shown]
Blood sample(s) for antibody testing are to be collected according to the time points specified in the Schedule of Activities [REDACTED] for the measurement of anti-AMG 340 binding antibodies. Samples testing positive for binding antibodies may be further characterized. Additional blood samples may be obtained to evaluate any anti-AMG 340 antibody mediated impact on safety, PK and/or PD, and efficacy during the study. At the end of treatment time point or potentially earlier, whole blood will be collected to further characterize a possible antibody response.

Subjects who test positive for antibodies at the final scheduled antibody time point and have clinical sequelae that are considered potentially related to an anti-AMG 340 antibody response will also be asked to return for additional follow-up testing. This testing is to occur approximately every 3 months from the final scheduled antibody time point and continue until: (1) antibodies are no longer detectable; or (2) the subject has been followed for a period of at least 1 year ( $\pm$  4 weeks) post administration of AMG 340.

More frequent testing or testing for a longer period of time may be requested in the event of safety-related concerns.

Refer to the Schedule of Activities (Section 1.3), as applicable, for specific time points, and the laboratory manual for detailed collection and handling instructions.

## **9. Statistical Considerations**

### **9.1 Statistical Hypotheses**

In Part A, a safe and tolerable dose of AMG 340 will have evidence of anti-tumor activity in subjects with mCRPC as measured by ORR. In Part B, AMG 340 will improve ORR in subjects with mCRPC to 20% compared with the reference ORR of 5%.

### **9.2 Sample Size Determination**

In Part A, at least 3 subjects are planned for enrollment into each cohort, with the goal of determining the MTD and/or RP2D of AMG 340. Approximately 60 subjects are anticipated in Part A; however, the total number of subjects in Part A will depend upon the occurrence of DLT events and how dose escalation progresses. If the unknown true toxicity rate/DLT rate is 33% in a given cohort, at least 2 DLTs are likely to be observed.

In Part B, up to 40 subjects will be enrolled to further evaluate safety and tolerability, to explore activity of AMG 340 and to evaluate the relationship between PD markers and PK, safety and clinical response. A sample size of 40 subjects was selected to achieve 92% power for testing the hypothesis on ORR at 1-sided alpha of 0.1 using the binomial exact test.

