## **5.1 Inclusion Criteria**

Subjects are eligible to be included in the study only if all of the following criteria apply:

- 101 Subject must be  $\geq$  18 years of age at the time of signing informed consent.
- 102 Subject has a history of pathologically confirmed prostatic adenocarcinoma.
- 103 Subject has history of metastatic disease.
- 104 Subject is chemically or surgically castrate (testosterone  $\leq$  0.5 ng/mL or 1.7 nmol/L). Subjects must continue on an LHRH/GnRH agonist or antagonist while on study unless they are surgically castrate.
- 105 Subject has received at least 2 lines of systemic therapy approved for mCRPC, with disease progression on the most recent systemic therapy as defined in PCWG3. Subjects should have previously been exposed to, intolerant of, ineligible for, or declined therapy with both a novel anti-androgen (eg, abiraterone, enzalutamide) and a taxane (eg, docetaxel).
- 106 Subject has an Eastern Cooperative Oncology Group (ECOG) Performance Status of  $\leq$  2 (see Section 11.8).
- 107 Subject has provided informed consent/assent prior to initiation of any study specific activities/procedures.
- 108 Subject must have adequate bone marrow function, defined as: absolute neutrophil count (ANC)  $\geq$  1500/mm^3; platelets  $\geq$  100 000/mm^3 (without platelet transfusion within 7 days from screening assessment); hemoglobin  $\geq$  9.0 g/dL (without blood transfusion within 7 days from screening assessment).
- 109 Subject must have an eGFR  $\geq$  50 mL/min as estimated by the MDRD formula. Note: Per FDA draft guidance, 'renal impairment is not likely to alter PK enough to justify dosage adjustment' for protein therapeutics  $>$  69 kDa, specifically including antibodies, such as AMG 340 (FDA 2020).
- 110 Subject must have total bilirubin  $\leq$  1.5  $\times$  upper limit of normal (ULN; except if the subject has a known diagnosis of Gilbert's syndrome, in which case bilirubin must be  $<$  3  $\times$  ULN). Aspartate aminotransferase (AST) and alanine aminotransferase (ALT) must be  $\leq$  3  $\times$  ULN (except if the subject has a known diagnosis of Gilbert's syndrome or liver metastases, in which case AST/ALT must be  $<$  5  $\times$  ULN).

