### **9.3 Populations for Analysis**

The following populations are defined:

Population	Description
PK	subjects who have received at least 1 dose of AMG 340 and have at least 1 PK sample drawn post dose

ADA	subjects who have received at least 1 dose of AMG 340 and have at least 1 ADA sample drawn post dose
RECIST 1.1 Evaluable	subjects who have received at least 1 dose of AMG 340, have measurable disease per RECIST 1.1 at baseline and have the opportunity to be followed for at least 6 weeks from start of AMG 340 treatment.
PSA Response Evaluable	subjects who have received at least 1 dose of AMG 340, have a measurable (ie, $> 0$ ) PSA at baseline, and have the opportunity to be followed for at least 9 weeks from start of AMG 340 treatment.
DLT-evaluable	subjects who are evaluable for DLTs. A subject is considered “DLT Evaluable” if the subject has completed at least the first full treatment cycle or has experienced a DLT during the first treatment cycle
Safety	subjects who have received at least 1 dose of AMG 340

ADA = antidrug antibody; DLT = dose limiting toxicity; PK = pharmacokinetic; PSA = prostate specific antigen; RECIST = Response Evaluation Criteria in Solid Tumor

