5.1.2 Secondary Endpoints Definitions

Objective Response per RECIST 1.1 (OR):

OR is defined as a partial response (PR) or complete response (CR) per RECIST 1.1, confirmed by a repeat assessment at least 4 weeks later. Subjects who do not experience a confirmed PR/CR or do not have any follow-up tumor assessments will be regarded as non-responders. This endpoint applies only to subjects with measurable baseline disease per RECIST 1.1.

Details for derivation of Objective Response per RECIST 1.1 are described in [Appendix B](#).

Overall Survival:

Overall survival is defined as the time from the date of Study Day 1 until death due to any cause:

OS time (Days) = date of death - Study Day 1 + 1.

Any subject not known to have died at the time of analysis will be censored based on the last recorded date on which the subject was alive.

PSA Progression:

PSA progression is defined as per PCWG3.

- After a decline in PSA from baseline to post-treatment, a PSA increase of $\geq 25\%$ and ≥ 2 ng/mL above the nadir (the lowest value up to the assessed visit date). This PSA progression must be confirmed by a second consecutive value ≥ 3 weeks later.
- No decline in PSA from baseline, a PSA increase of $\geq 25\%$ and ≥ 2 ng/mL from baseline at or beyond 12 weeks after treatment initiation.

Radiographic Progression:

A radiographic progression occurs if either of the following occurs:

- Progressive disease per RECIST 1.1 occurs.
- Bone disease progression as per PCWG3 occurs. Bone disease progression for the first post-treatment bone scan (e.g. Week 8) showing two or more additional lesions relative to screening/baseline must be confirmed by the next bone scan (e.g. Week 16) showing two or more additional lesions relative to first post-treatment bone scan (e.g. Week 8) at least 6 weeks later. Bone disease progression for scans after the first post-treatment scan (e.g. Week 16) showing two or more additional lesions relative to the first post-treatment bone scan (e.g. Week 8) can be confirmed by second scan showing persistence of the additional lesion relative to the first post-treatment scan (e.g. Week 8) at least 6 weeks later.

PSA Progression-free Survival (PSA PFS):

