6.3 Study-specific Analysis Sets

6.3.1 RECIST 1.1 Evaluable Analysis Set

RECIST 1.1 Evaluable Analysis Set is defined as all subjects who have received at least 1 dose of AMG 340, have measurable disease per RECIST 1.1 at baseline, and have the opportunity to be followed for at least 6 weeks from start of AMG 340 treatment. Subjects who stopped disease assessments prior to 6 weeks will be included in this analysis set if the **data snapshot date** is at least 6 weeks after their first study dose date.

This analysis set is used for the analysis of the radiographic-measured endpoints of objective response and duration of response (radiographic).

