^b Following the confirmation of PD at the subsequent bone scan, the overall radiological visit response of progression for the visit will be programmatically derived as PD using the progression date (previous bone scan date where new lesion first seen) captured on the eCRF

^c For subjects with non-measurable disease only at baseline.

^d For subjects with RECIST 1.1 response of CR, PR, SD, PD, NE or Missing.

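### The 92% power for ORR belongs to 40 evaluable subjects, not 40 enrolled; the test that sizes Part B is missing from the ORR analysis; and the Part A DLT sentence fails for cohorts of 3 or 4

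*Protocol*

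**What the plan says.** **Part B size.** Protocol 9.2 and SAP 3.2 say: "A sample size of 40 subjects was selected to achieve 92% power for testing the hypothesis on ORR at 1-sided alpha of 0.1", using the exact binomial test. Protocol 9.1 and SAP 2.2 set the rates at 20% against a reference of 5%. The same paragraph uses 40 as an enrolment ceiling: "In Part B, up to 40 subjects will be enrolled to further evaluate safety and tolerability".

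**Who is analysed for ORR.** The RECIST 1.1 Evaluable population in Protocol 9.3 must "have measurable disease per RECIST 1.1 at baseline and have the opportunity to be followed for at least 6 weeks". SAP 5.1.2 says of objective response: "This endpoint applies only to subjects with measurable baseline disease per RECIST 1.1". SAP 6.3.1 and Table 9-1 assign ORR to that set.

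**Who may enter.** On extent of disease, inclusion criterion 103 asks only: "Subject has history of metastatic disease". No inclusion or exclusion criterion asks for measurable disease. The plan provides for subjects without it: footnote c of SAP Table 14-4 reads "For subjects with non-measurable disease only at baseline", and Protocol Table 11-6 gives response rules for non-target disease only.

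**How ORR is analysed.** Protocol 9.4.2.2 and SAP Table 9-1 give the proportion with an exact 95% Clopper-Pearson interval. Neither mentions a test, an alpha or a responder threshold, and SAP Section 10 does not list the test as dropped.

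**Part A.** Protocol 9.2 and SAP 3.2 plan at least 3 subjects per cohort. They then state that two or more DLTs are likely if the true rate is 33%, without naming a cohort size. Protocol 4.1.1 sets a minimum of 3 and allows up to 6 concurrently.

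**The concern.** ORR of 20% against 5% is the only numerical reason given for the size of Part B. If 40 means enrolled and some subjects have no measurable disease, the test runs on fewer than 40, and the stated power belongs to a larger sample than the one analysed. No allowance is stated.

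The test behind the power figure also has no place in the analysis sections. A reader of the results would see only a 95% interval, which corresponds to a one-sided level of 0.025 rather than 0.1. The critical value moves with the evaluable number, so a rule not written down in advance invites a choice after the data are seen.

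The DLT sentence describes what a cohort can be expected to show. If it fails at the minimum cohort size given in its own paragraph, it overstates what 3 subjects can reveal.

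**Working it through.** **1. The stated power**

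Inputs: p0 = 0.05 and p1 = 0.20 (Protocol 9.1); n = 40, one-sided alpha 0.1, exact binomial (Protocol 9.2). The critical value c is the smallest k with P(X ≥ k | n, p0) ≤ 0.1.

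- P(X ≥ 4 | 40, 0.05) = 0.138, above 0.1.
- P(X ≥ 5 | 40, 0.05) = 0.048, so c = 5.
- Power = P(X ≥ 5 | 40, 0.20) = 0.924.

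The 92% reproduces.

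**2. Which 40?**

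The evaluable set has three conditions. Under Protocol 5.3 a subject counts as enrolled only once dosed, so the dosing condition removes nobody. The primary analysis falls 6 months after the last Part B enrolment, and SAP 6.3.1 keeps subjects who stop assessments early, so the 6-week condition should remove nobody either. Measurable disease is the condition that can shrink the denominator.

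Exact power by evaluable number:

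| Evaluable n | Reject at | Power |
|---|---|---|
| 40 | ≥ 5 | 92.4% |
| 38 | ≥ 5 | 90.1% |
| 36 | ≥ 5 | 87.3% |
| 35 | ≥ 4 | 93.9% |
| 33 | ≥ 4 | 91.9% |
| 32 | ≥ 4 | 90.7% |
| 30 | ≥ 4 | 87.7% |
| 28 | ≥ 4 | 84.0% |
| 24 | ≥ 4 | 73.6% |
| 22 | ≥ 3 | 84.6% |
| 20 | ≥ 3 | 79.4% |

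Power is saw-toothed: it rises when the critical value drops by one.

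The documents give no measurable share. Assume a share s, so that the evaluable number M is Binomial(40, s). Mean power is then the sum over m of P(M = m) × power(m):

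| Assumed share | Mean power |
|---|---|
| 95% | 90.4% |
| 90% | 90.4% |
| 85% | 90.8% |
| 80% | 89.6% |
| 75% | 87.0% |
| 70% | 83.6% |
| 60% | 78.5% |
| 50% | 74.6% |

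**3. Test against interval at n = 40**

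- 5/40: the test rejects 5%. The 95% Clopper-Pearson interval is 4.2% to 26.8% and includes 5%.
- 6/40: the test rejects, and the interval, 5.7% to 29.8%, excludes 5%.
- At 4 or fewer, neither excludes 5%.

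The two therefore differ at exactly 5 responders. P(X ≥ 6) is 0.8387 at a true ORR of 20% and 0.0139 at 5%. The chance of landing on 5 is 0.9241 − 0.8387 = 0.085 at 20%, and 0.0480 − 0.0139 = 0.034 at 5%.

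**4. The DLT sentence**

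P(X ≥ 2 | n, 0.33) = 1 − 0.67^n − n × 0.33 × 0.67^(n−1). For n = 3: 1 − 0.3008 − 0.4444 = 0.2548.

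| Subjects | P(at least 2 DLTs) |
|---|---|
| 3 | 25.5% |
| 4 | 40.1% |
| 5 | 53.2% |
| 6 | 64.2% |
| 10 | 89.2% |

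Taking likely to mean more than 50%, the sentence holds from 5 subjects.

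**The case against.** The case for leaving the text alone has four parts.

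- **The 92% is right, and the label is merely unclear.** This stands. A reader might infer that the power was miscalculated or that Part B is materially underpowered. The documents support neither: the figure reproduces, and mean power stays near 90% at assumed shares of 80-95%. Losses to 75-84% need shares of 50-70%, for which the documents give no basis. Even a fall in the evaluable number need not cost power: 33 to 35 evaluable give 91.9-93.9%.
- **The interval is estimation.** This also stands. A reader might infer that the 95% interval is the decision rule and that power is really 83.9%. No section makes it a rule, and a 95% interval beside a one-sided 0.1 test is not a contradiction. What remains is that the interval cannot stand in for the test.
- **The test is defined elsewhere.** Null, alternative, alpha, sidedness and method are all in Protocol 9.1 and 9.2 and the matching SAP sections. With the analysis set, they fix the critical value for any evaluable number. True, but the analysis sections never say that the test will be performed or reported.
- **The DLT sentence names no cohort size.** It holds for 5 or 6, and Table 4-1 runs to 10. So it is incomplete rather than false across the design. It still fails at the minimum of 3 in its own paragraph.

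**Conclusion.** The concern holds in limited form and is minor.

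- The 92% is correct for 40 evaluable subjects and not assured for 40 enrolled, because measurable disease is required for the ORR analysis but not for entry, and no allowance is stated. How much power is lost depends on the measurable share, which is an assumption: at 80-95% the loss is about 2 to 3 points, at 70% about 9, and at 50% about 18.
- The exact test that sizes Part B is missing from the ORR analysis. At n = 40 the reported interval would point the other way at 5 responders only.
- The DLT sentence is not true for cohorts of 3 or 4. It changes no dose decision, since escalation follows Table 4-1.

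ORR is a secondary endpoint, and both plans mark primary efficacy analysis as not applicable. SAP 7.2 also allows for Part B not going ahead, in which case the first two points lapse.

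**What to change.** 1. **Protocol 9.2 and SAP 3.2, Part B.** State that 92% applies to 40 RECIST 1.1 evaluable subjects, and add the table of critical values and power by evaluable number under step 2 of the working. Keep both peaks and troughs, so that the loss looks neither steeper nor flatter than it is. No added enrolment.
2. **Protocol 9.4.2.2 and SAP Table 9-1, objective response.** For Part B, add the exact one-sided 0.1 binomial test of ORR against 5% in the RECIST 1.1 Evaluable set, with the critical value set by the actual evaluable number. Keep the 95% Clopper-Pearson interval as the estimate.
3. **Protocol 9.2 and SAP 3.2, Part A.** Replace the DLT sentence with: *At a true DLT rate of 33%, the probability of at least 2 DLTs is 25% with 3 evaluable subjects, 40% with 4, 53% with 5, 64% with 6 and 89% with 10.*

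The cost is wording, one small table and one test line in the analysis. No subjects are added, and no dosing or escalation rule changes.
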